4.1.5 Confounder or Bias Adjusted Analyses

Confounding will be controlled through the use of propensity scores, based on the values of covariates at the time of IUD insertion. The propensity score estimates the probability that a given patient will be exposed conditional on measured covariates and can serve as a summary confounder variable. Propensity scores can perform better than conventional regression methods when the number of events relative to the number of potential confounders is small, because rather than having to model the events with many variables, which may lead to overfitting of the outcome model, one can instead model the exposure, for which the larger number of exposed people provides sufficient data to accommodate a rich model (Cepeda et al., 2003). This advantage may be important in this study, given the low number of expected events, particularly for uterine perforation, within this study.

The steps in estimating adjusted exposure effects are listed as follows:

1. Derive variables that will be considered for inclusion in the propensity score models.
2. Assess balance between exposure groups in the sample.
3. Identify key variables to be included in the propensity score model.
4. Estimate propensity scores and assess the overlapping area among all exposure groups.
5. Calculate weights, normalize the weights, and examine the normalized weights.
6. Assess balance between exposure groups in the weighted sample.
7. Add to the propensity score model additional terms (e.g., interaction or higher order terms) of the covariates that do not balance.
8. Fit the new propensity score model and estimate the propensity scores.
9. Repeat steps 5-8 until all the key covariates are balanced.
10. Estimate the exposure effect that accounted for the confounders via weighting.

Propensity scores for exposure variables will be estimated by fitting a logistic regression model (for dichotomous exposure variables) or a multinomial logistic regression model (for exposure variables with more than two categories). The dependent variable in the propensity score model is exposure status (e.g., women breastfeeding at the time of IUD insertion vs. not breastfeeding at the time of IUD insertion).

Breastfeeding status, postpartum timing, and IUD type will be included within the propensity score model (as independent variables when not the dependent variable). Other covariates will be assessed

for inclusion in propensity score models based on association with the study outcome (Brookhart et al., 2006); thus, analysts will not be blinded to the outcome. Baseline covariates to be considered for inclusion are listed in Sections 3 and 4.6. Categorical variables will be assessed for inclusion based on indicator coding of the categories. Continuous variables (including integer count variables) will be assessed for inclusion as continuous, dichotomous, and categorical (i.e., indicator coded) variables, as appropriate. Covariates will be included in the propensity score model if the crude hazard ratio is greater than 1.11 or less than 0.90. Additional confounders will be selected for inclusion within propensity score models if at least a 10% change in the hazard ratio of the exposure-outcome relationship occurs when adjusting for that variable, including at least a 10% change in any level of a categorical exposure variable relative to the referent group (> 52 weeks postpartum for postpartum period).

From the fitted logistic regression models, propensity scores and the overlap weights (Li et al., 2018) will be estimated for each IUD insertion. Overlap weighting is a relatively new weighting scheme to adjust for confounding effects. Overlap weights belong to a class of balancing weights, including commonly used weights for inverse probability weighting. Li et al. (2018) mathematically proved and verified in simulations that the overlap weights minimize asymptotic variance among balancing weights. Other advantages of overlap weights over inverse probability weighting include perfect balance for means and bounded weights avoiding explosive weights or the need for arbitrary truncation. In addition, the overlap weights focus on the naturally comparable “overlap” population, and therefore propensity score ‘trimming’ for a common support area is not necessary. The overlap weights have been applied in observational studies, for example, Schneider et al. (2001), although the term “overlap weights” was not established at that time.

For dichotomous exposure variables, the propensity score is the probability of being exposed. The propensity score for patient (insertion) i is denoted as $e_i = \Pr(Z_i = 1|X_i)$, where Z_i denotes the exposure (1= exposed, 0 = unexposed), and X_i denotes a vector of baseline covariates. The overlap weight for patient i is defined as follows:

$$w_i = \begin{cases} 1 - e_i, & Z_i = 1 \\ e_i, & Z_i = 0 \end{cases}$$

For categorical exposure variables with more than two levels, the propensity scores will be estimated for each patient and exposure level. Consider an exposure variable with K exposure groups ($K > 2$). The propensity score for patient i and exposure k , $k=1, \dots, K$, denoted as e_{ik} , is the probability that a patient will be exposed to exposure k conditional on measured covariates X_i :

$$e_{ik} = \Pr(Z_i=k|X_i), \text{ with } \sum_{k=1}^K e_{ik} = 1$$

The overlap weight for patient i given exposure k is defined as follows:

$$w_{ik} = \frac{1}{e_{ik} \sum_{k=1}^K \frac{1}{e_{ik}}}$$

The overlap weights will be normalized by multiplying the weights by $\frac{n}{\sum_{i=1}^n w_i}$, where n is the total sample size. The extreme weights (min, max), mean, and standard deviation of the normalized weights will be assessed, although extreme weights are not expected to be an issue with overlap weights because the overlap weights are bounded.

The distribution of propensity scores among exposed (e.g., breastfeeding at the time of IUD insertion) and unexposed (e.g., not breastfeeding at time of IUD insertion) patients will be examined using histograms with kernel smoothing to identify the overlapping area. However, all patients will be included in the analysis when applying overlap weights. The overlap weights put the strong focus on those patients with the highest overlap in their propensity scores and therefore avoid the need for trimming the population.

The balance across exposure groups will be assessed before and after weighting. The distribution of each variable will be compared between categories of the exposure variable, and balance parameters (i.e., standardized differences) (Austin and Stuart, 2015) will be calculated. Pairwise balance parameters (e.g., pairwise standardized differences) will be used for the categorical exposure variable in which each category will be compared to the referent group (> 52 weeks postpartum for postpartum period). The maximum of the pairwise standardized differences will also be reported. The balance between exposure groups will be assessed overall and within each data source. If the groups are unbalanced on key covariates after application of overlap weighting, then the logistic regression model will be revised by including interaction terms (e.g., with data source), higher order terms, or transformation of variables, and the covariate balance between the groups overall and within each data source will be re-evaluated based on the revised model. When satisfactory balance between the exposed and unexposed groups is achieved, the weighting will be incorporated in modeling for confounder-adjusted outcome assessments (Section 4.1.5). The exposure groups are considered balanced if the standardized difference is less than 0.20 (generally considered small) (McCaffrey et al., 2013). If satisfactory balance is difficult to achieve, which is not expected for overlap weighting, matching of patients between groups may be considered.

Separate propensity score models will be developed for exposure-outcome pairings related to breastfeeding status, postpartum period, IUD type, and menorrhagia for uterine perforation and IUD expulsion. The list of propensity score models is provided in Section 9.3. Sections 6.2 and 6.3 includes additional information for specific objectives. In general, the selection of covariates for inclusion in propensity score models will be conducted only using first insertions. The association between baseline covariates and outcomes (crude hazard ratio) will be assessed only using the complete study population, which includes only the first IUD insertion for each woman. No covariate selection will be conducted for *subsequent* insertion models. Instead, for each specific pairing, covariates and terms included in the final propensity score model for first insertions will be included in the propensity score model for subsequent insertions. Additionally, IUD insertion count (the sequential number) may be included in the propensity score model if it is not balanced across exposure groups for *subsequent* insertions. Propensity scores and weights will be estimated from the corresponding propensity score models.

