3.1 Exposures

- *Pregnancy delivery date* is the date on which delivery occurred
- *Breastfeeding status* at the time of IUD insertion: breastfeeding status is defined for every insertion based on whether there is any evidence of breastfeeding (including any breastfeeding or pumping across a 24 hour period) at the time of IUD insertion. For postpartum \leq 52 weeks, breastfeeding status is defined as Yes, No, or Undetermined. For postpartum $>$ 52 weeks, including no evidence of a live birth in the past 52 weeks, breastfeeding is not assessed (and will be classified as No when used as a covariate).
- *IUD type*: three-level categorical variable indicating the type of IUD inserted:
 - LNG-IUD: Mirena, Liletta, Skyla, Kyleena
 - Copper IUD: ParaGard, other copper
 - Unknown IUD type

- *Menorrhagia*: diagnosis of menorrhagia assessed in two variables
 - As an exposure: indicator variable (0 = No, 1 = Yes) for whether the patient was diagnosed with menorrhagia in the year (365 days) prior to or on the index date
 - As a covariate within other exposure assessments: four-level categorical variable for whether the patient was diagnosed with menorrhagia
 - Diagnosed in the year prior to or on the index date, but not diagnosed before that time
 - Not diagnosed in the year prior to or on the index date, but was diagnosed before that time
 - Diagnosis recorded within the year prior to or on the index date and also before that time
 - No diagnosis of menorrhagia within the data

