4.3 Handling of Missing Data

Missing data will be treated as missing, unless specified otherwise, and no imputations will be performed. In database analyses of previously collected data, if information on a particular binary variable, such as a disease diagnosis or a medication, is available in the database, patients are assumed to have the factor only if there is evidence for its presence (i.e., absence of information will be taken to mean absence of the condition or medication).

Where appropriate, variables will include a “missing” category for analyses. Consequently, data analyses will be conducted using all women and insertions to the extent possible with respect to their observed available data (i.e., the IUD insertion will not be included in an analysis if missing data for any variable in that analysis, except where “missing” is a separate category for the analysis).

Counts of missingness will be reported in descriptive analysis of categorical variables, and percentages for the nonmissing categories will be based on the number of nonmissing values. For continuous variables, the number of nonmissing values will be reported, and descriptive summaries

will be based on the number of nonmissing values. In addition, the percentage of patients or insertions with missing data will be provided for breastfeeding and IUD type.

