5.1 Assignment of Analysis Sets

The complete study population will be defined by the study inclusion and exclusion criteria. However, subsets of the complete study population will be used to address certain study objectives. The analysis sets for the *first eligible IUD insertions* are outlined in Table 2. The analysis sets for subsequent IUD insertions will be defined in the same way for the corresponding IUD insertions.

Table 2. Women Included in Analysis Sets 1 and/or 2

Event in Electronic Health Record	Postpartum Status	Breastfeeding Status ^a		
		Yes	No	Undetermined
Delivery in the past year (52 weeks)	≤ 6 weeks	1, 2	1, 2	1
	> 6 weeks and ≤ 14 weeks	1, 2	1, 2	1
	> 14 and ≤ 52 weeks	1, 2	1, 2	1
No evidence of delivery in the past year	No delivery in the past 52 weeks	NA	1	NA

NA = not applicable.

^a The numbers indicate the analysis set numbers.

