5.1.1 Analysis Set 1: Complete Study Population

This analysis set will include women with eligible insertions based on study inclusion and exclusion criteria outlined in Section 3 and in the study protocol. This analysis set will include women with missing data for breastfeeding status and/or IUD type for the insertion. The missing data within breastfeeding status and IUD type may be considered a separate group in the analyses (e.g., when developing the propensity score model for postpartum period).

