6.2.1 Analysis for Primary Objectives

In the following groups of women, the adjusted hazard ratios for uterine perforation will be evaluated:

- Objective 1. Women who were breastfeeding at the time of the first observed IUD insertion versus those who were not breastfeeding at the time of the first observed IUD insertion.
- Objective 2. Women who had a first observed IUD insertion within different time periods postpartum (i.e., ≤ 6 weeks, > 6 weeks and ≤ 14 weeks, > 14 weeks and ≤ 52 weeks) versus those who had a first observed IUD insertion late in the postpartum period (more than 52 weeks postpartum, including those without recorded delivery in the past 52 weeks).

For objective 1, analyses will be conducted using Analysis Set 2 (breastfeeding status is available). For objective 2, analyses will be conducted using Analysis Set 1 (complete study population). Both analyses will use only the first observed IUD insertion.

Cox regression models will be used to obtain crude hazard ratios overall and by data source with assessment of the proportional hazards assumption (Section 4.1.4).

Confounding effects will be adjusted using the propensity score weighting method (Section 4.1.5). After developing the propensity score model, calculating the weights, and assessing the balance between exposure groups in the weighted sample, adjusted hazard ratios will be estimated using the weighted Cox regression model as described in Section 4.1.6. Additionally, the interaction effect between the data source and the exposure will be assessed after adjustment for confounding. The interaction will be assessed by including terms for exposure, database, and the interaction between the database and the exposure in the weighted Cox models. A type 3 group test for the interaction terms will be conducted. If the test is statistically significant ($P < 0.05$), then the interaction terms will be retained in the final model, and the adjusted hazard ratios will be reported for each data source. If the interaction terms are not statistically significant, then the interaction terms will be removed, and the overall adjusted hazard ratios (the main effect) will be reported as the results of the primary analyses.

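### Forcing breastfeeding into the four-level timing propensity score confines the adjusted hazard ratios of primary objective 2 to non-breastfeeding women, which the SAP does not state and protocol Table 4 does not reflect

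*SAP*

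**What the plan says.** SAP 4.1.5 puts three variables into every propensity model without screening: "Breastfeeding status, postpartum timing, and IUD type will be included within the propensity score model (as independent variables when not the dependent variable"). Breastfeeding therefore enters the four-category timing models, numbered 2, 6, 11 and 14 in SAP 9.3.

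For women beyond 52 weeks or without a recent live birth, SAP 3.1 says "breastfeeding is not assessed (and will be classified as No when used as a covariate"). SAP Table 2 (section 5.1) agrees: in the no-delivery row, Yes and Undetermined are marked not applicable.

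On undetermined status, SAP 5.1.1 keeps these women in Analysis Set 1 and says missing values "may be considered a separate group in the analyses (e.g., when developing the propensity score model for postpartum period"). SAP 4.3 has the general rule that "the IUD insertion will not be included in an analysis if missing data for any variable in that analysis", unless missing is its own category.

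On who is analysed, SAP 6.2.1 says "For objective 2, analyses will be conducted using Analysis Set 1 (complete study population"), and Table Layout 2.2 carries the same label. SAP 4.1.5 notes in general terms that overlap weights concentrate on comparable women, and then says: "However, all patients will be included in the analysis when applying overlap weights".

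Protocol 9.5 (Table 4) gives power for objective 2 at a hazard ratio of 2.0 as 73%, >99% and 73%, using 168,750, 202,500 and 168,750 insertions.

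**The concern.** Breastfeeding = Yes is a structural zero in the referent group. The propensity model cannot give a finite coefficient for it, and the overlap weight removes these women from all three postpartum bands. Nothing in the SAP says that this happens.

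Objective 2 is a primary objective of a postmarketing requirement, and the protocol's rationale records regulatory interest in both time since delivery and US breastfeeding practice. A reader of the adjusted column in Table 2.1 would apply the timing hazard ratios to breastfeeding women, who contribute almost nothing to them. The crude and covariate-adjusted Cox results keep those women, so a difference between the results could be read as confounding when it partly reflects a different population. The stated power also counts women whom the weighted analysis removes.

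**Working it through.** **Counts (protocol 9.5).** First insertions: 225,000. Within 52 weeks postpartum: 30%, or 67,500. Breastfeeding status known for 60,000, split 60:40: 36,000 Yes and 24,000 No. Undetermined, by subtraction: 67,500 − 60,000 = 7,500. Timing allocation 5:20:5:70: 11,250, 45,000, 11,250 and 157,500. The documents give no breastfeeding mix by band, so the same mix in each band is an assumption.

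**Weight.** SAP 4.1.5 gives w_k = (1/e_k) / Σ(1/e_l), summed over the four groups. If the referent probability tends to 0, the sum tends to infinity, and the weight tends to 0 in each of the other three groups.

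- Not breastfeeding (Undetermined separate): e = 4,000, 16,000, 4,000 and 157,500, each over 181,500. Weights in the three postpartum bands: 0.44, 0.11, 0.44.
- Breastfeeding, referent probability 0.0001: weights 0.0006, 0.00015, 0.0006. Share of each band's weight: 36,000 × 0.0006 / (36,000 × 0.0006 + 24,000 × 0.44) = 0.2%.
- Breastfeeding, referent probability 0.001: 2.0% of each band's weight.

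Fitting the multinomial model to the expected counts confirms that there is no finite limit. The referent probability for breastfeeding women is 0.00087 at iteration 5, 0.000043 at iteration 8 and 0.000006 at iteration 10.

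**Women who lose weight.** 36,000 / 67,500 = 53% if Undetermined is merged with No. (36,000 + 7,500) / 67,500 = 64% if it is a separate level, since that level is also empty in the referent.

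**Balance limit.** SAP 4.1.5: "The exposure groups are considered balanced if the standardized difference is less than 0.20". Before weighting, the standardized difference for breastfeeding is 0.533 / √(0.533 × 0.467 / 2) = 1.51. After weighting with a 0.2% share it is 0.002 / √(0.002 × 0.998 / 2) = 0.06, a pass. Only a fit stopped as early as 0.001 would come near the limit: 0.02 / √(0.02 × 0.98 / 2) = 0.20.

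**Power.** Schoenfeld, two-sided 0.05: power = Φ(ln 2 × √(D p(1−p)) − 1.96), with D = insertions × risk and p = exposed share. Plan's figure first: D = 168,750 × 0.0013 = 219.4 and p = 5/75 give 72.6%; D = 263.3 and p = 20/90 give 99.7%. Both match Table 4. Then with only the women who keep weight, against 157,500 referents:

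| Basis | Full bands | Undetermined merged with No (5,250 / 21,000 / 5,250) | Undetermined separate (4,000 / 16,000 / 4,000) |
|---|---|---|---|
| Schoenfeld, 1.3 per 1,000 | 73 / >99 / 73% | 43 / 93 / 43% | 34 / 85 / 34% |
| Schoenfeld, 0.9 per 1,000 | not applicable | 32 / 81 / 32% | 25 / 71 / 25% |
| Per-group events, 1.3 per 1,000 | 92 / >99 / 92% | 69 / 99 / 69% | 58 / 97 / 58% |

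The 0.9 is the risk protocol 9.5 quotes for women not breastfeeding. The per-group formula splits the same total events in the ratio 2n₁ : n₀ and uses variance 1/d₁ + 1/d₀. Expected events at 1.3 per 1,000 fall from 14.6 to 6.8 or 5.2 in each 5% band, and from 58.5 to 27.3 or 20.8 in the middle band.

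**Collapsed contrast.** For ≤ 14 versus > 14 weeks, a breastfeeding woman's propensity is (11,250 + 45,000) / 67,500 = 0.83, so she keeps weight.

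**The case against.** Much can be said for the plan.

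- The analysis-set label names who enters the analysis, and it is right for the counts and crude hazard ratios in Table Layout 2.2. The SAP does say that overlap weights favour comparable women. This stands, but the SAP never says that breastfeeding women as a class fall outside.
- The SAP's steps check unweighted balance, propensity overlap and weights before any effect is estimated, and section 6 has a rule for cells below 10. These could expose the empty cell. They prescribe no remedy, and the sparse-cell rule permits leaving the cell unchanged.
- A reader might infer that Table 4 was miscalculated. It was not: it is correct for its inputs. It belongs to protocol v2.0 (June 2018), where breastfeeding was not forced into the propensity score; SAP v2.0 (October 2018) added that. SAP section 4 refers sample size back to the protocol without an update.
- The 225,000 already allows about 15% for missing data and trimming. That is well below 53% to 64% of postpartum women, although subtracting 7,500 undetermined women may partly count missing data twice.
- The power figures move with the risk and formula: the formula alone lifts the full 5% bands from 73% to 92%. Restated power also changes no decision in a retrospective study of all available data. Both are fair, and they argue for a range rather than one number.
- A reader might infer that all timing results lose breastfeeding women. They do not. Crude hazard ratios, the unweighted Cox sensitivity analysis, the 14- and 36-week contrasts and objective 28 are not restricted in this way.

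**Conclusion.** The point holds as one of stated population and stated power, and should be fixed. The adjusted four-level hazard ratios of objectives 2, 23, 31 and 32, and the four-level parts of 18 and 26, describe non-breastfeeding women only. Breastfeeding women hold 2% or less of each postpartum band's weight, although they are about 53% of the women in those bands.

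On the plan's own method, power at a hazard ratio of 2.0 is 34% to 43% in each 5% band and 85% to 93% in the middle band. The 5% bands lose most on every basis tried; the middle band's loss is material on the plan's method and small on the per-group one. These figures rest on an equal breastfeeding mix per band and a 1-year risk. Events after year 1 would raise them; weight variation from other covariates would lower them.

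The documents do not support the stronger inference that the adjusted estimate is invalid: among women not breastfeeding it remains a coherent comparison. Nor do they support dropping breastfeeding from the primary propensity score as the cure. With the protocol Table 2 relative risk of 3.3 and 53% to 60% of postpartum women breastfeeding, omission alone could produce an apparent timing ratio of 1 + 0.533 × 2.3 = 2.2 to 1 + 0.6 × 2.3 = 2.4.

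**What to change.** 1. In SAP 4.1.5, state that breastfeeding = Yes is a structural zero in the referent for models 2, 6, 11 and 14. Fit the four-level propensity model and weights among women classified as not breastfeeding, rather than rely on a coefficient that does not converge.
2. Fix the coding of Undetermined in advance. A separate level agrees with SAP 5.1 and 5.1.1; these women then stay in Analysis Set 1 for counts and crude results and, like breastfeeding women, carry no weight in the adjusted comparison. Excluding them from Analysis Set 1 would conflict with those sections.
3. In 4.1.5, 6.2.1 and the adjusted column of Table Layout 2.2, write: *The adjusted four-level hazard ratios apply to women classified as not breastfeeding at insertion, including referent women, who are classified No by rule.* Avoid wording that says referent women were recorded as not breastfeeding, because their status is not assessed. Keep the complete-population label for counts and crude hazard ratios.
4. For each timing category, report effective sample size, weighted events and share of weight by breastfeeding status.
5. Restate objective 2 power on the women who keep weight, as a range, with the assumed mix, risk and formula.

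The cost is SAP text, an explicit restriction that the weights already impose in effect, and a few extra counts; no new data are needed. The downside is a narrower stated population and less favourable stated power for a primary objective.

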9	Interaction of breastfeeding and early vs. late postpartum (breastfeeding/ \leq 14 weeks; breastfeeding/ $>$ 14 weeks; no breastfeeding/ \leq 14 weeks; no breastfeeding/ $>$ 14 weeks [referent])	Uterine perforation

^a Secondary objectives include dichotomization of “early” and “late” postpartum categories. Separate propensity score models will not be *developed* for these objectives. Rather, the propensity scores calculated with the four-category variable will be used, and the distribution of scores will be collapsed into the categories for each secondary objective. Assessment of distributions of propensity scores will be performed within these collapsed categories.

Propensity scores for dichotomous exposure variables will be estimated by fitting a logistic regression model that incorporates data source (i.e., KPNC, KPSC, KPWA, or RI) and measured potential predictors of exposure as independent variables (all baseline variables in Section 9.3.1 will be considered). The dependent variable in the propensity score model is exposure status (e.g., women breastfeeding at the time of IUD insertion vs. not breastfeeding at the time of IUD insertion).

Propensity scores for the categorical variable (i.e., timing of postpartum insertion) will be estimated by fitting a multinomial logistic regression model that incorporates data source (i.e., KPNC, KPSC, KPWA, or RI) and measured potential predictors of exposure as independent variables (all baseline variables in Section 9.3.1 will be considered). The dependent variable in the propensity score model is exposure category (i.e., ≤ 6 weeks postpartum; > 6 and ≤ 14 weeks postpartum; > 14 and ≤ 52 weeks postpartum; > 52 weeks postpartum [referent]).

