Crude IRD (95% CI)		x.xx (x.xx, x.xx)	Reference	x.xx (x.xx, x.xx)	Reference
Adjusted IRD (95% CI)		x.xx (x.xx, x.xx)	Reference	x.xx (x.xx, x.xx)	Reference

CI = confidence interval; IRD = incidence rate difference; IRR = incidence rate ratio; IUD = intrauterine device.

^a Adjusted via weighted estimation of the rates using overlap weights derived from the same propensity score models as those developed for adjustment of the hazard ratios.

^b Incidence rates and incidence rate differences are expressed per 1,000 person-years.

Generated using xxxx.sas on xxxxxxxx.

Programming note 1: Generate tables x.1 for uterine perforation and x.2 for IUD expulsion.

**Table Layout 11. Effect Modification of Breastfeeding Status and Postpartum Status on Uterine Perforation;
 Analysis Set: Breastfeeding Status Available, First IUD Insertion;
 Database: Pooled**

	Postpartum Status	Breastfeeding Status		HR (95% CI) Breastfeeding (Yes vs. No)
		Yes	No	
Number of events/ insertions	14 weeks or less	xx/xx	xx/xx	
	> 14 weeks or no delivery	xx/xx	xx/xx	
Crude HR	14 weeks or less	x.xx (x.xx, x.xx)	x.xx (x.xx, x.xx)	x.xx (x.xx, x.xx)
	> 14 weeks or no delivery	x.xx (x.xx, x.xx)	1.00 (Reference)	x.xx (x.xx, x.xx)
	HR (95% CI) 14 weeks or less vs. > 14 weeks or no delivery	x.xx (x.xx, x.xx)	x.xx (x.xx, x.xx)	
Adjusted HR	14 weeks or less	x.xx (x.xx, x.xx)	x.xx (x.xx, x.xx)	x.xx (x.xx, x.xx)
	> 14 weeks or no delivery	x.xx (x.xx, x.xx)	1.00 (Reference)	x.xx (x.xx, x.xx)
	HR (95% CI) 14 weeks or less vs. > 14 weeks or no delivery	x.xx (x.xx, x.xx)	x.xx (x.xx, x.xx)	
	Type 3 group test for interaction of breastfeeding status and postpartum status			P = 0.xxxx

CI = confidence interval; HR = hazard ratio; IUD = intrauterine device.

Note: Crude HRs were estimated from the Cox model including breastfeeding status, postpartum status, and their interaction. Adjusted HRs were estimated from the Cox models including breastfeeding status, postpartum status, and their interaction, weighted using overlap weights.

Generated using xxxx.sas on xxxxxxx.

Table Layout 12.1. Effect Modification of IUD Type on Breastfeeding Status and Uterine Perforation;
Analysis Set: Breastfeeding Status Available, First IUD Insertion;
Database: Pooled

Modifier IUD Type	Exposure Breastfeeding Status	Number of Events	Number of Insertions	Crude HR (95% CI)	Adjusted HR (95% CI)
LNG-IUD	Yes	xx	xx	x.xx (x.xx, x.xx)	x.xx (x.xx, x.xx)
	No	xx	xx	1.00 (Reference)	1.00 (Reference)

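### The SAP does not carry over the protocol's inclusion of data source in the propensity models, so the pooled IRR/IRD and the effect-modification results may be unadjusted for site

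*SAP*

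**What the plan says.** Protocol 9.7.1.3.2 describes two kinds of propensity model. The logistic model for dichotomous exposures "incorporates data source (i.e., KPNC, KPSC, KPWA, or RI) and measured potential predictors of exposure as independent variables". The model for postpartum timing is estimated by "fitting a multinomial logistic regression model that incorporates data source (i.e., KPNC, KPSC, KPWA, or RI"), again alongside the measured predictors. In both, data source is a component of the model and not one of the candidates to be screened.

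SAP 4.1.5 sets a different rule. The fixed terms are given as "Breastfeeding status, postpartum timing, and IUD type will be included within the propensity score model (as independent variables when not the dependent variable"). For the rest, "Covariates will be included in the propensity score model if the crude hazard ratio is greater than 1.11 or less than 0.90", and further confounders enter "if at least a 10% change in the hazard ratio of the exposure-outcome relationship occurs when adjusting for that variable". On the candidates it says: "Baseline covariates to be considered for inclusion are listed in Sections 3 and 4.6". The Database variable does stand in Section 3, but in 3.8 under Other Parameters. Table Layout 1 also puts site under that heading, next to continuous enrollment, which a footnote there says is not a baseline covariate.

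The note to Table Layout 6 repeats the SAP rule without data source. Section 7 of the SAP records that the three named confounders became fixed terms in version 2.0 and does not mention data source.

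**The concern.** Site can confound these comparisons. Protocol 9.9 says the sources obtain breastfeeding status in different ways. Protocol 9.2 says the algorithms differ in terminology between sites. Table 3 of the protocol gives EHR start dates from 2001 to 2009.

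Under the protocol, site would be handled by the weights wherever the weights are used. Under the SAP, site enters the weights only if it passes a data-dependent screen, and possibly not at all if Database is not treated as a candidate. That matters little where the outcome model contains site. It matters where the weights do all the adjustment: the pooled weighted rates, and the Cox models that contain only exposure, modifier and their interaction. The effect-modification analyses are planned on pooled data only (SAP 6.2.2.5), so no by-site result would show a problem.

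**Working it through.** **1. Where site is adjusted under the SAP.**

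| Analysis | Site in the outcome model? | Site in the weights? |
|---|---|---|
| Main HR tables (Layouts 2.1, 2.2) | Yes: exposure and site | Only if screened in |
| IRR/IRD, by-site rows (Layout 10) | Not needed within a site | Not needed |
| IRR/IRD, pooled row (SAP 4.1.8, 4.1.10, 6.2.2.3; objectives 17, 25) | No term or stratum | Only if screened in |
| Effect modification (SAP 6.2.2.5, 6.3.1; objectives 28 to 32) | No | Only if screened in |

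For objective 28 the note to Layout 11 reads: "Adjusted HRs were estimated from the Cox models including breastfeeding status, postpartum status, and their interaction, weighted using overlap weights". The notes to Layouts 12.1 and 12.2 have the same structure with IUD type.

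**2. Event count, anchored to the plan's own power.** Primary objective 1: 60,000 × 0.0013 = 78 events. Schoenfeld power at HR 2.0 with 60:40 allocation is Φ(ln 2 × √(78 × 0.6 × 0.4) − 1.96) = Φ(2.999 − 1.96) = 0.851, against a stated 85%. The complete population then gives 225,000 × 0.0013 = 292.5 perforations.

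**3. Does the crude HR screen reliably bring site in?** Site sizes come from Protocol 9.4.1 to 9.4.4: about 100,000 (KPNC), 80,000 (KPSC), 15,000 (KPWA) and 5,700 (RI), or shares of 0.498, 0.399, 0.075 and 0.028. Poisson events by site were simulated (200,000 replicates) with three indicators against a reference site, assuming no true site difference.

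| Events | Chance that no site indicator leaves 0.90 to 1.11 |
|---|---|
| 292.5 (planned perforations) | about 5% |
| 585 (double) | 10 to 12% |
| 2,250 (1% incidence, assumed) | 37 to 46% |
| 11,250 (5% incidence, assumed) | 85 to 93% |

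The ranges are over the choice of reference site. At 292.5 events with KPNC as reference, a single indicator passes 40% of the time (KPSC) to 78% (RI), so site could also enter only in part. With no true site difference, leaving site out does no harm. The table shows only that entry is decided by the data and is not guaranteed.

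**4. Size if site is left out.** Let s be the site share, p the exposure prevalence in the site and r the site rate, with a true IRR of 1 in every site. Then

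pooled IRR = [Σ s·p·r / Σ s·p] ÷ [Σ s·(1−p)·r / Σ s·(1−p)].

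Prevalences are assumed, since the documents give none by site: KPNC/KPSC at 25%/35%, 20%/40% or 15%/45%, and 30% elsewhere. KPNC is the reference.

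- r = 1, 1.11, 1.11, 1.11: pooled IRR 1.011, 1.023, 1.035.
- r = 1, 1.11, 0.90, 0.90: pooled IRR 1.011, 1.022, 1.034.

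A two-site check at the edge of the band agrees: (0.65 × 1.11 + 0.35) / (0.35 × 1.11 + 0.65) = 1.032, and with 60/40 shares 1.021.

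**The case against.** The strongest reply is that the SAP has several routes by which site can be handled, and that the documents give little sign that site matters.

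- The 10% change-in-estimate rule is a second gate. It is aimed at the case where a near-null crude site HR hides confounding. This stands: if Database is screened, site stays out only when adjusting for it moves the exposure HR by less than 10%.
- SAP 4.1.5 allows unbalanced models to be revised with interaction terms, giving data source as the example, and checks balance within each source. This suggests the authors had data source in mind. It does not guarantee entry, and balance of covariates within a site is not balance of site itself.
- Protocol 9.9 reports no significant differences in population characteristics or outcome prevalence across sources in the validation study, and Protocol 9.2 says the algorithms capture the same concepts. This stands as a reason to expect a small effect. It does not show that there is no confounding.
- Table Layout 10 also gives adjusted IRR and IRD by site. This stands; only the pooled row is exposed.
- For perforation, the chance that no site indicator passes the crude screen is only about 5% in the simulation. This stands too, but partial entry remains possible and the figure assumes that Database is screened.

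A reader might infer a bias of 4 to 6%, from (0.65 × 1.11 + 0.35 × 0.90) / (0.35 × 1.11 + 0.65 × 0.90) = 1.065, or 1.043 with 60/40 shares. That sets two sites 1.11 / 0.90 = 1.23 apart. With either as reference, the other would fail the band and site would enter. The figure needs a third site as reference lying between them, and the SAP names no reference site.

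**Conclusion.** The discrepancy is real and undocumented. As written, the SAP can leave the pooled adjusted IRR and IRD and the effect-modification hazard ratios without any adjustment for site. The expected size is modest: about 1 to 4% in the pooled IRR, resting on assumed exposure prevalences by site, KPNC as reference and site rate ratios within 0.90 to 1.11. The effect-modification results were not sized separately.

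If Database is not treated as a candidate, neither gate applies. Under the same assumed prevalences, rate ratios of 1.5 to 2.0 for the other sites against KPNC would give a pooled IRR of 1.044 to 1.235. The documents give no reason to expect ratios that large.

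Two stronger readings should be set aside. A reader might infer that the primary results are affected; they are not, because both primary objectives are estimated from a weighted Cox model that includes site. A reader might also infer that the protocol expressly puts data source in every propensity model. Its multinomial sentence names only postpartum timing, so model 9 (breastfeeding by early versus late postpartum, objective 28) is covered only by implication.

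This is a low-priority correction, worth making because it costs almost nothing.

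**What to change.** State in SAP 4.1.5 and in the note to Table Layout 6 that data source is included, without screening, in all 15 propensity models listed in SAP 9.3, naming model 9 explicitly. The cost is three indicator terms in each logistic model and three per logit in each multinomial model. The variable is already held at the coordinating center, and no sample size or power figure changes.

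If the sponsor prefers to keep the screen, the alternative is to add site to the effect-modification Cox models, stratify the pooled IRR and IRD by site, and record the departure from the protocol in SAP Section 7.
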